## 4. STUDY DESIGN

### 4.1. Overall Design

A business decision was made by Pfizer to terminate the C4971003 study. The reason for study termination is not due to any safety concerns or requests from regulatory authorities. As a result of this decision, Phase 1b will be discontinued after the last participant last visit and Phase 2 of the study will not be initiated.

This is a multicenter, international, Phase 1b/2 study of different doses of PF-07901801 in combination with tafasitamab and lenalidomide in participants with R/R DLBCL who have completed at least 1 line of systemic treatment (at least 1 containing an anti-CD20 therapy), who are not candidates for high dose therapy/ASCT. See [Section 1.2](#) for design schema.

The Phase 1b will be conducted in approximately 20 participants. The objectives of the Phase 1b are to evaluate the safety and tolerability, PK, PD of PF-07901801 in combination with standard doses of tafasitamab and lenalidomide and to select doses for Phase 2.

An escalation/de-escalation approach guided by mTPI-2 will be used in Phase 1b to determine the PF-07901801 MTD or RP2D (2 dose levels) in combination with tafasitamab and lenalidomide, for further evaluation of the fixed doses for efficacy and safety in Phase 2.

A minimum of 2 to 4 DLT-evaluable (Section [4.3.4](#)) participants is required at each tested dose level of PF-07901801. Approximately 6 to 9 DLT-evaluable participants will be treated at the MTD or highest safe tested dose level for PF-07901801 before proceeding to Phase 2.

Following completion of Phase 1b of the study, if at least 2 doses of PF-07901801 are considered tolerable, 2 doses will be selected for further evaluation in the Phase 2. In Phase 2 of the study, participants must have been exposed to 1 but no more than 2 lines of prior therapies. Approximately 50 participants will be randomized 1:1 into 2 selected doses of PF-07901801 in combination with standard doses of tafasitamab and lenalidomide to further characterize the safety and tolerability of the combination and assess the efficacy of each dose level.[27](#)

If only 1 dose of PF-07901801 is considered tolerable after Phase 1b because of safety or other reasons, approximately 25 participants will be treated at the selected fixed dose in the Phase 2 of the study.

Enrollment of participants with prior CAR-T will initially be limited to approximately 3 to 6 participants; after review of all available safety data and determined safe, enrollment of further participants will continue. Post CAR-T participants are to provide local CD19 expression result (if available) and tissue for future central testing (both must be a sample after CAR-T and prior to C1D1).

At the sponsor's discretion proceeding to Phase 2 will be determined upon completion of Phase 1b. The totality of data including efficacy, safety, PK, PD, biomarker, and other considerations will be used to determine the recommended doses for further development in the Phase 2.

For Phase 1b and Phase 2, PF-07901801 and tafasitamab treatment will continue until PD, non-tolerable toxicity or death while lenalidomide will be administered for up to 12 cycles; if a participant with documented PD per Lugano criteria continues to experience clinical benefit, study treatment with PF-07901801 and tafasitamab may continue until no longer clinically benefiting as per a risk-benefit assessment by the investigator (see [Section 8.2](#)).

## 4.2. Scientific Rationale for Study Design

### 4.2.1. Diversity of Study Population

Although the incidence of DLBCL is higher in Caucasians versus African-Americans (82% vs 7.33%), African-Americans are diagnosed at an average age 10 years younger compared to Whites, are more likely to have more advanced disease at the time of diagnosis, and have a worse overall survival rate. To ensure African-Americans are adequately represented in this trial, efforts will be made to include sites that serve African-American communities. In addition, efforts will be made to initiate educational and recruitment campaigns focused on the African-American community if needed.

### 4.2.2. Dose Level Review Meeting

During the Phase 1 DLT period, a DLR team, composed by sponsor personnel, including at least one medically qualified member, together with the investigators that have enrolled treated study participants in the specific cohort will review cumulative safety data after the last participant in each cohort has been followed for at least 28 days from the first dose of the combination therapy. This review is separate from the ongoing safety assessments routinely performed by the sponsor (Section [9.4.5](#)).

### 4.2.3. Choice of Contraception/Barrier Requirements

There are no data on the use of tafasitamab in pregnant women. However, IgG is known to cross the placenta and tafasitamab may cause fetal B-cell depletion based on pharmacological properties.

Studies to evaluate the developmental toxicity of PF-07901801 have not been conducted.

Lenalidomide is known to cause risk for severe manifestations of developmental toxicity in humans. Therefore, the use of a highly effective method of contraception is required (see [Appendix 4](#)). The conditions of the PPP for lenalidomide that have been set by the manufacturer ([Section 10.4.5](#)) must be fulfilled for all participants unless there is reliable evidence that the participant does not have childbearing potential. Refer also to the local prescribing information for contraception guidelines for lenalidomide.

The duration of the contraception required after the last dose of study intervention is 4 weeks for male participants and 90 days for female participants; and contraception should be initiated 4 weeks before the start of study intervention (see [Appendix 4](#) for details).

#### **4.2.4. Collection of Retained Research Samples**

Retained Research Samples will be collected and stored for further analyses which may, for example, provide greater understanding of the study intervention.

#### **4.3. Justification for Dose**

##### **4.3.1. Dosing Regimens of PF-07901801**

Phase 2 of the study will not be initiated per business decision made by Pfizer (protocol amendment 2).

As of 12 December 2021 (Data Safety Update Report cut-off date), in the FIH Study C4971001, PF-07901801 has been administered to 67 participants with advanced R/R lymphoma as monotherapy in 8 different dose-escalation cohorts. Dose cohorts ranging from 0.05 mg/kg to 18 mg/kg (equivalent to 3.75 mg to 1350 mg for a 75 kg person, respectively) QW were well-tolerated with no MTD reached. The combination of PF-07901801 and tafasitamab plus lenalidomide has not previously been evaluated. The proposed starting dose of PF-07901801 (4 mg/kg QW for C1 to C3 then Q2W for C4 and onwards) in combination with full dosing of tafasitamab and lenalidomide is expected to provide limited target engagement for PF-07901801 antitumor activity while it is 4.5 times lower relative to the maximum administered dose of PF-07901801 (18 mg/kg QW) for monotherapy in the FIH Study C4971001. Preliminary analyses showed sustained target engagement at higher dose levels with dose-dependent increase in receptor occupancy durability at the end of dosing interval. For example, receptor occupancy for doses below 4 mg/kg QW decreased to substantially lower levels at the end of the dosing interval, eg, below 10% at 1.0/2.0 mg/kg QW dose level.

In Phase 2 of the current study C4971003, a fixed dosing approach will be used instead of body weight (BWT) based dosing approach used in the FIH study C4971001 based on the following rationales:

- BWT was found not to be a significant covariate on linear and non-linear clearance in the Population PK model.

$AUC_{\text{tau}}$  normalized by total dose (mg) provided a lower inter-patient variability (2-31%) compared to the observed  $AUC_{\text{tau}}$  (23-48%) based on BWT dosing, suggesting a potential lower inter-patient variability in PK with fixed dosing compared to BWT based dosing. Fixed doses to be explored in the Phase 2 will be determined upon completion of Phase 1b. The totality of data including efficacy, safety, PK, PD, biomarkers, and other considerations will be used to determine the recommended doses (Low dose and High dose) for further dose optimization in the Phase 2.

##### **4.3.2. Dosing regimen of Tafasitamab and Lenalidomide**

Tafasitamab will be administered at 12 mg/kg IV according to the following schedule; each cycle has 28 days.

- C1: Days 1, 4, 8, 15 and 22.

- C2 and C3 (QW): Days 1, 8, 15 and 22.
- $\geq$ C4 (Q2W): Days 1 and 15.

This is the recommended dosage and dosing schedule in the USPI and EU SmPC of tafasitamab in combination with lenalidomide for the treatment of adult patients with R/R DLBCL, who are not eligible for ASCT.

Lenalidomide will be administered 25 mg PO daily on Days 1 through 21 of each 28-day cycle for up to 12 cycles. This is the dosage regimen used in the L-MIND study, which supported the accelerated and conditional approval of tafasitamab in combination with lenalidomide for the treatment of adult patients with R/R DLBCL NOS, including DLBCL arising from low grade lymphoma, and who are not eligible for ASCT. To reduce PK and safety assessment variability, participants with creatinine clearance  $<60$  mL/min will be excluded in the Phase 1b of the study since lenalidomide exposure and the risk for higher hematological adverse reactions or hepatotoxicity increase in this population.

#### 4.3.3. Criteria for Dose Escalation

The provisional dose levels of PF-07901801 to be evaluated are listed in Table 3.

**Table 3. Provisional Dose Levels PF-07901801 in Dose-Escalation**

Cohort	Dose (mg/kg)	Increment (%)
1 (DL1)	4 mg/kg QW for C1 to C3 then Q2W	X
2 (DL2)	10 mg/kg QW for C1 to C3 then Q2W	150%
3 (DL3)	18 mg/kg QW for C1 to C3 then Q2W	80%

Additional PF-07901801 doses, dose levels and/or dosing frequency or schedule may be explored.

Each cycle is 28 days. QW = Days 1, 8, 15 and 22. Q2W = Days 1 and 15.

The dosing schedule may also be adjusted to expand a dosing cohort to further evaluate safety, PK, and/or PD findings at a given dose level or to add cohorts to evaluate additional dose levels. The study procedures for these additional participant(s)/cohort(s) will be the same as that described for other study participants/cohorts.

If a participant experiences a non-DLT event that requires a dose held per dose-modification guideline additional participants may be enrolled. If DL3 is not tolerated an additional cohort (DL4) may be explored at a dose intermediate to DL2 and DL3.

If after one cohort dose level has been determined safe and the subsequent dose cohort is pending completion of its DLT period, new eligible participants may be enrolled and 'backfilled' into the safe, prior cohort. For these additional participants, their data will contribute to safety and efficacy analyses but they will not participate in the DLT algorithm.

#### 4.3.4. Dose Limiting Toxicity Definition

The DLT observation period will be the first 28-day cycle of treatment in each participant. A DLT is defined as any of the following TEAEs that are considered by the investigator at least possibly related to any or all of the combination study treatments. Note that any AEs for which the relationship to study treatment cannot be ruled out should be considered possibly related. All toxicities that occur during the study will be actively managed following the standard of care per local institutional practice unless otherwise specified in the protocol.

A participant is classified as DLT evaluable if they either 1) receive at least 80% of the planned dose of PF-07901801 and at least 75% of the planned dose of tafasitamab and lenalidomide and have received the majority of scheduled safety assessments during the DLT observation period; or 2) have experienced a DLT. The percentage of drug received is calculated as the percentage of the actual total amount of drug(s) administered during the DLT observation period in relation to the planned total amount of drug(s) to be administered for the DLT observation period.

- A participant failing to meet these criteria may be replaced. If the participant has missed a minority of safety assessments due to emergency situations (eg, site accessibility issues, inability to go to an external lab, etc.), the DLR team may judge the participant evaluable, depending on the abundance of the available data.

For the purpose of dose escalation, any of the treatment-related AEs defined in Section 4.3.4.1, occurring in the first 28 days of treatment that in the opinion of the investigator cannot be reasonably attributed to the participant's underlying disease, concomitant medications or preexisting conditions are considered DLTs.

Severity of AEs will be graded according to CTCAE v5.0. For those events involving a worsening of a baseline abnormality, a DLT must represent a clinically significant (in the opinion of the investigator after discussion with the sponsor) shift from baseline:

##### 4.3.4.1. Hematological DLTs

- G4 thrombocytopenia ( $<25,000/\mu\text{L}$ ) lasting  $\geq 72$  hours or a platelet count  $\leq 10,000/\mu\text{L}$  at any time, unexplained by underlying disease.
- $\geq \text{G3}$  thrombocytopenia associated with  $\geq \text{G2}$  bleeding, unexplained by underlying disease.
- G4 anemia, unexplained by underlying disease.

Prophylactic use of erythropoietin or blood products are not allowed during the DLT period in Phase 1b.

- G4 neutropenia lasting  $\geq 7$  days, unexplained by underlying disease.
- G3 febrile ( $\geq 38.3^\circ\text{C}$ ) neutropenia lasting  $\geq 7$  days, unexplained by underlying disease.

- G4 febrile neutropenia unexplained by underlying disease.

Note: Prophylactic use of granulocyte-colony stimulating factors is not permitted during the DLT period of Phase 1b, but they may be used to treat treatment emergent neutropenia as per prescribing information.

#### 4.3.4.2. Non-Hematologic DLTs

- Any treatment-related  $\geq$ G3 non-hematologic toxicity (see below for specifications applying to special circumstances) with the following exceptions:
  - G3 nausea, vomiting and diarrhea that improve to G2 or better within 72 hours after supportive care;
  - Transient G3 fatigue lasting  $\leq$ 7 days;
  - G3 AEs that recover to baseline or G1 within 3 days;
  - Transient asymptomatic  $\geq$ G3 laboratory abnormalities considered not clinically significant following agreement between investigators and the sponsor's medical monitor and starting to recover within 72 hours of their onset with standard supportive care;
  - Hypersensitivity that can be controlled with medical treatment and resolves to asymptomatic ( $\leq$ G1) within 72 hours.
- Other  $\geq$ G2 PF-07901801-related non-hematologic toxicities that, in the opinion of the investigator, require a dose reduction or discontinuation of PF-07901801 may be considered a DLT.

#### 4.3.5. Maximum Tolerated Dose

MTD is defined as the highest dose with true DLT rate within the EI of the target DLT rate. The target DLT rate is 0.3, the EI is (0.25, 0.35).

#### 4.4. End of Study Definition

The end of the study is defined as the date of the last follow-up visit of the last participant in the global study.

A participant is considered to have completed the study if they have completed all periods of the study, including the last follow-up visit.

#### 5. STUDY POPULATION

This study can fulfill its objectives only if appropriate participants are enrolled, including participants across diverse and representative racial and ethnic backgrounds. A prescreening tool for study recruitment purposes will include collection of information that reflects the enrollment of a diverse participant population including, where permitted under local

regulations, age, sex, and race, and ethnicity. The following eligibility criteria are designed to select participants for whom participation in the study is considered appropriate. All relevant medical and nonmedical conditions should be taken into consideration when deciding whether a particular participant is suitable for this protocol.

Prospective approval of protocol deviations to recruitment and enrollment criteria, also known as protocol waivers or exemptions, is not permitted.

Pfizer will review eligibility criteria verified by the investigator or qualified designee to confirm that participants meet study eligibility criteria before they are randomized into the study. The randomization approval process will be initiated for a participant after an Informed Consent Document has been signed and the investigator or qualified designee has assessed the participant as eligible. The randomization approval will be based on review of CRF/system data.

### **5.1. Inclusion Criteria**

Participants are eligible to be included in the study only if all of the following criteria apply:

#### **Age and Sex:**

1. Participants aged 18 years of age or older (or the minimum age of consent in accordance with local regulations) at Screening.
  - Refer to [Appendix 4](#) for reproductive criteria for male ([Section 10.4.1](#)) and female ([Section 10.4.2](#)) participants, and PPP ([Section 10.4.5](#)).

#### **Disease Characteristics:**

2. Histologically confirmed, measurable relapsed and/or refractory DLBCL NOS, T cell/histiocyte rich large B-cell lymphoma; or EBV positive DLBCL, according to the 5th edition of the WHO Classification of Lymphoid Neoplasms. Further, follicular lymphoma grade 3b, or composite lymphoma with a DLBCL component with a subsequent DLBCL relapse.
  - Participants with evidence of histological transformation to DLBCL from an earlier diagnosis of low grade lymphoma (ie, an indolent pathology such as follicular lymphoma, marginal zone lymphoma, chronic lymphocytic leukemia) are eligible if relapsed or refractory to at least one line of therapy for DLBCL (for primary refractory, see exclusion criterion #2 below).
3. Participant characteristics:
  - Not a candidate per investigator or unwilling to undergo high dose chemotherapy and subsequent autologous stem cell transplant or unable to receive approved CAR-T therapy (eg, logistical limitations).

- Measurable disease: at least 1 site of measurable, PET-avid disease per Lugano 2014 classification (index lesion: >1.5 cm in the longest diameter for nodal, >1.0 cm in the longest diameter for extranodal disease).

4. Prior systemic treatment regimen:

- Must include an anti-CD20 containing regimen:
  - Phase 1b: at least 1 prior line of systemic therapy.
  - Phase 2: at least 1 but no more than 2 prior lines of systemic therapy.

For both phases: induction, ASCT and consolidation will be considered one line of therapy; bridging therapy prior to CAR-T and CAR-T treatment will be considered together as one line of therapy.

- If exposed to prior CD19-targeting CAR-T therapy:
  - Last CAR-T infusion must have been completed >90 days prior to C1D1.
  - Provide CD19 expression test at Screening as per local lab, if available, and must provide a tissue sample for retrospective central testing (see also inclusion criterion #8 and [Section 8.7.8](#)). CD19 positivity is not required.

5. Adequate organ function:

- Hematology (with no transfusion or growth factor support for at least 2 weeks prior to C1D1):
  - ANC  $\geq$ 1,000/ $\mu$ L.
  - Platelet count  $\geq$ 90,000/ $\mu$ L.
  - Hemoglobin  $\geq$ 8 g/dL.
- Hepatic function:
  - T bili  $\leq$ 2.0  $\times$  ULN. Participants with documented Gilbert's syndrome are eligible for this study providing the direct bilirubin is  $\leq$ ULN.
  - ALT and AST  $\leq$ 2.5  $\times$  ULN.
- Renal function:
  - Phase 1b: Estimated creatinine clearance  $\geq$ 60 mL/min per local assessment.
  - Phase 2: Estimated creatinine clearance  $\geq$ 30 mL/min per local assessment.

Note for Phase 2: for creatinine clearance  $\geq 30$  mL/min and  $< 60$  mL/min, lenalidomide is to be started with a reduced dose of 10 mg daily.

6. ECOG performance status  $\leq 2$ .

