## Study Population

Adult participants ( $\geq 18$  years of age) with histologically confirmed measurable relapsed or refractory DLBCL not eligible for stem cell transplantation will be enrolled in the study.

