## Key Inclusion Criteria

- Histologically confirmed DLBCL; relapsed or refractory disease.
- Participant is not a candidate for or is unwilling to undergo high dose chemotherapy and subsequent stem cell transplant or is unable to receive approved chimeric antigen receptor (CAR-T) therapy.
- Prior treatment with at least 1 line of systemic therapy (for phase 2: at least 1 and no more than 2 lines of systemic therapy). Prior therapy must include an anti-CD20 containing regimen.
- Adequate hematologic, hepatic and renal function.
- Eastern Cooperative Oncology Group (ECOG) performance status  $\leq 2$ .
- Participants are able to provide a tumor tissue sample collected before start of treatment (fresh or archival).

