**Ethical Considerations**

[figure not shown]
Patients with R/R DLBCL who are not candidates for ASCT due to age or co-morbidities have limited treatment options and poor prognosis. The combination of tafasitamab and lenalidomide has shown increased response and progression-free survival in patients with R/R DLBCL, leading to conditional approval. By engaging overlapping as well as different mechanisms with the combination of tafasitamab and lenalidomide, PF-07901801 is expected to increase anti-tumor activity in patients with R/R DLBCL. Further, available safety data of PF-07901801 as a single agent in patients with DLBCL suggest that it may be combined with other approved agents without significantly increasing their toxicity. Possible overlapping toxicity with the proposed regimens include neutropenia and thrombocytopenia; to minimize

risks, participants will be monitored frequently, including weekly blood tests for their first 8 weeks of treatment.

Therefore, taking into consideration the complementary mechanisms of action of PF-07901801 with tafasitamab and lenalidomide as well as the safety profile of PF-07901801, this combination may offer a more efficacious and tolerable treatment option for older patients or patients with co-morbidities that are not candidates for high dose chemotherapy and/or ASCT.

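### Inclusion criterion 3 makes lack of CAR-T access sufficient by itself, so a transplant-eligible, willing patient can enter a trial described as transplant-ineligible

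*Protocol*

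**What the plan says.** Criterion 3 in Protocol Section 5.1 is met by a patient whom the investigator judges not to be a candidate, or who is "unwilling to undergo high dose chemotherapy and subsequent autologous stem cell transplant or unable to receive approved CAR-T therapy (eg, logistical limitations". Logistical limits are given as an example of the last item. The Key Inclusion Criteria in the Synopsis (Section 1.1) carry the same chain and repeat the verb before the last item: "unwilling to undergo high dose chemotherapy and subsequent stem cell transplant or is unable to receive approved chimeric antigen receptor (CAR-T) therapy".

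The population statements are narrower:

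- **Synopsis, Study Population:** patients with "relapsed or refractory DLBCL not eligible for stem cell transplantation will be enrolled in the study". The protocol title says the same in substance.
- **Overall Design (Synopsis and Section 4.1):** patients "who are not candidates for high dose therapy/ASCT".
- **SAP Sections 2 and 2.3:** patients not eligible for, or not candidates for, high-dose therapy and ASCT.
- **Section 2.1, Study Rationale:** adds patients who are not willing to have ASCT. It does not mention CAR-T access.
- **Synopsis, Ethical Considerations:** "Patients with R/R DLBCL who are not candidates for ASCT due to age or co-morbidities have limited treatment options and poor prognosis".

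**The concern.** Eligibility criteria decide who enters; titles and design summaries only describe. Here the operative rule is wider than every description of it. The extra route does not depend on transplant status, so it can admit people for whom ASCT remains an available option.

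Two things are at stake. First, the ethics case is argued for patients whom age or comorbidity rules out of transplant, and it does not address someone who could have one. Second, Phase 1b OR, CR, DoR and PFS are summarised for everyone treated (Protocol Section 9.4.1, SAP Section 5.2). A reader would take them as results in transplant-ineligible disease. The SAP baseline tables (Sections 6.6.1.3 and 6.6.1.4) report prior transplant and prior CAR-T, but not why ASCT was not used, so a mixed population could not be recognised from the planned output.

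**Working it through.** The protocol gives no figure to reproduce here. The check is one of logic, followed by simple shares.

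**1. The criterion as a rule.** Let A = not an ASCT candidate per investigator, B = unwilling to have ASCT, C = unable to receive approved CAR-T. As written, criterion 3 is A or B or C.

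| Patient | A | B | C | A or B or C (as written) | A or B |
|---|---|---|---|---|---|
| Not a candidate | true | – | – | met | met |
| Candidate, declines ASCT | false | true | – | met | met |
| Candidate, willing, no CAR-T access | false | false | true | **met** | **not met** |

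Only the third row changes, so the outcome turns on the second 'or'. The repeated verb in the Synopsis confirms that C stands as its own alternative.

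**2. Does anything else remove the third patient?** Section 5.1 opens with "Participants are eligible to be included in the study only if all of the following criteria apply", so another numbered criterion could close the gap. None does. The remaining inclusion criteria cover age and reproductive requirements, histology, prior therapy, organ function, performance status, recovery from earlier treatment and tissue. Of the exclusions, only criterion 6 concerns transplant, and it addresses past procedures: any prior allogeneic transplant, or ASCT within 12 weeks.

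**3. Is such a patient plausible on the protocol's own account?** Yes.

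- Section 2 says patients relapsing after first-line treatment may go on to induction chemotherapy and ASCT.
- Phase 1b accepts patients after one prior line. Exclusion 2 removes primary refractory disease, which leaves later relapses.
- Phase 1b requires creatinine clearance of at least 60 mL/min.
- Section 2 describes CAR-T as confined to major academic centers, so C is not hard to meet.

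**4. Does it reach the analysis?** The Phase 1b primary estimand (Protocol Section 9.2.1.1, SAP Section 2.2.1) defines its population by the inclusion and exclusion criteria and says these reflect the target population. A patient admitted through C alone is therefore inside the estimand population if DLT-evaluable, and in the Safety Analysis Set once treated.

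**5. Weight of one such participant.** Inputs are from Protocol Section 9.6: about 20 participants in Phase 1b, and about 6 to 9 DLT-evaluable at the MTD or highest safe tested dose.

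- Share of Phase 1b: 1/20 = 5%.
- Share of that dose level: 1/9 = 11% to 1/6 = 17%.

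These are shares per hypothetical entrant, not estimates of how many there were.

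**The case against.** The strongest reply has five parts.

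**The CAR-T clause has a rationale.** Section 2 says limited availability, turn-around time and toxicity restrict CAR-T use and that new treatments are needed. That explains why the clause exists. It does not reconcile a stand-alone CAR-T route with a population stated in terms of ASCT.

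**Transplant-eligible patients enter anyway.** Those who decline ASCT qualify through B and would still qualify after the CAR-T clause is moved. This stands. The difference is that the Study Rationale acknowledges that group, while no population statement acknowledges entry through C alone. The title, Study Population, Section 4.1 and the SAP still need to be aligned with B.

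**There are safeguards.** Section 5 asks that all relevant conditions be weighed in judging suitability, and the sponsor reviews eligibility. These are soft: the first is discretionary, and the second confirms only that the criteria are met, which this patient does.

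**The reach is small.** This also stands. Phase 2 will not be initiated and its endpoints will not be analysed. Phase 1b efficacy is secondary, descriptive and already mixed, with no cap on prior lines and post-CAR-T participants allowed.

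**No benchmark is lost.** A reader might infer that the trial forfeits its one comparator, the single-arm study of tafasitamab plus lenalidomide (ORR 60%) in patients not eligible for high-dose chemotherapy or ASCT. The documents do not support that. Section 2 also cites polatuzumab vedotin with bendamustine and rituximab (response 45%) and a CAR-T trial (83%). The protocol has no formal hypothesis test and plans no comparison with any of them.

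**Conclusion.** The contradiction is real and rests on the text alone. Criterion 3 and its Synopsis counterpart admit a transplant-eligible, willing patient who lacks CAR-T access; the title, Study Population, Overall Design and SAP place that patient outside the trial, and the Study Rationale does not bring that patient in.

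Its practical size is limited and unknown. It touches Phase 1b only, mainly the interpretation of descriptive OR, CR, DoR and PFS. The figures of 5% and 11-17% per entrant assume that at least one such patient enrolled, which the documents neither state nor imply. A reader might infer that the Phase 1b results are biased or that the DLT rate is invalid. Neither follows: no count by entry route is given, and the DLT estimand takes its population from the criteria as written. The point is worth correcting because it concerns who may enter and costs little, not because it endangers the primary analysis.

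**What to change.** 1. **Reconcile the criterion with the population.** In Section 5.1 criterion 3 and the Synopsis Key Inclusion Criteria, take the CAR-T clause out of the 'or' chain so that lack of CAR-T access is not sufficient by itself. Keep it as a recorded characteristic. It should not become an added mandatory condition: that would bar ASCT-ineligible patients who could receive CAR-T, and it would fit poorly with the post-CAR-T participants whom Sections 4.1 and 5.1 admit.
2. **Or state the wider population.** If the sponsor meant CAR-T access to be a stand-alone route, the title, Study Population, Overall Design, Study Rationale, SAP and Ethical Considerations must say so. Which rule was intended is for the sponsor to settle.
3. **In either case, acknowledge refusal of ASCT.** Align the title, Study Population, Section 4.1 and SAP Section 2 with the 'unwilling' branch already in Section 2.1.
4. **Record and list the branch each Phase 1b participant met**, so that OR, CR, DoR and PFS can be read for the stated population.

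Cost: a wording change in two places for the criterion, consistency edits to the population statements, and one CRF field or listing. While enrolment is open, step 1 would slow accrual slightly, because transplant-eligible, willing patients without CAR-T access could no longer enter. If enrolment has ended, step 4 is the useful part that remains.
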